Participants randomized to the bCBT direct referral arm will have information obtained from the assessment (e.g. responses from the PHQ-9, level of physical pain experiencing, any comorbid psychiatric diagnoses, and their contact information forwarded to a study-consented CBOC provider (via encrypted email), who will schedule the patient for an initial treatment session. The assessment information is provided to inform the clinician on areas of difficulty the patient may be experiencing to aid in recommendation of treatment modules. Participants and clinicians will work collaboratively to determine the modality of treatment – telephone, face-to-face, or a mixture. All bCBT sessions are deliverable by telephone but clinicians and patients may opt to have face-to-face meetings. Data on telephone and face-to-face meetings will be collected and examined in treatment analyses. Clinicians will be encouraged to offer 6 weekly treatment sessions but may alter the intensity or "dose" of treatment, based on Veteran depression response scores and/or provider/patient decision to discontinue treatment. For completers, the final treatment "dose" may include between 3 and 9 sessions over a course of up to 4 months. Clinicians will be asked to complete the PHQ-9 during treatment sessions to assess treatment

response. Regular PHQ-9 administration is consistent with bCBT and measurement-based care. Data on treatment sessions will be documented using template CPRS clinician notes to facilitate clinician documentation, allowing the study team to monitor and extract important treatment information during and after the trial.

[figure not shown]

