During active treatment, clinicians will be asked to discuss depressive symptoms and response with participants as part of the treatment process. Providers will be encouraged to deliver bCBT as long as it remains appropriate for any given patient. If a patient is discovered to have additional needs that make the use of bCBT inappropriate, the clinician can opt to seek additional or alternative care for the patient. The presence of severe depression, substance abuse, and comorbid PTSD or anxiety disorders could all require the clinician to change or add treatments. At the end of the 4 month treatment period, clinicians will be encouraged but not required to discontinue treatment. For patients who reach the response criterion, clinicians will introduce the potential for treatment discontinuation. For patients who do not reach the targeted depression goal by the final session (6th session), clinicians will work with the patient to determine whether additional sessions would be helpful. The provider will have the option to continue care or refer the patient to other therapies that are not a part of the research study based on their clinical judgment.

“Rapid” responders will be asked to stay in treatment for a minimum of 3 sessions. For nonresponders, treatment may be extended up to a maximum of 9 sessions.

Figure 1. Response to bCBT Treatment and Determination of Treatment Ending

ARM #2: Enhanced Usual Care

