treatment). Antidepressant medications will be evaluated in both the treatment and usual care groups at all assessment time points, affording the study an opportunity to evaluate whether assignment to the treatment group impacted receipt of medications. Participant self-report data will allow for global estimates of non-VA medication use. Health Service Use: Health-service-use will be collected for each participant to control for non-study encounters and healthcare services. Service use will be collected from VA medical records as well as a patient self-reported non-VA service-use questionnaire. Health service information will be collected via VHA national and regional databases. The study team will obtain all relevant approvals (e.g. DART) prior to data extraction. Data will be collected on the frequency and type of inpatient hospitalizations and outpatient medical and mental health encounters. Outpatient mental health care use will be monitored and used as a covariate.

Treatment Variables Intensity/dose of bCBT will be defined as the total number of sessions attended. Session (telephone/in-person) and module type will be collected to examine for impact on outcomes. These data will be collected via note templates and chart review procedures using CAPRI. Treatment Expectancy will be assessed using the Expectancy Rating Scale (ERS).⁵⁵ The ERS includes 4 items that assess how logical treatment seems, the patient's confidence undergoing treatment and recommending it to others, and expectations for treatment's success. Therapist Rating of Patient Engagement and Adherence will be collected following the last session of treatment.

Therapists will be asked to rate the overall level of patient engagement and adherence (2 items), using a 10-point Likert-style format, ranging from not at all engaged/adherent to fully engaged/adherent. Working Alliance will be assessed using patient and therapist report forms of the Working Alliance Inventory - Short Form (WAI-S). The WAI-S consists of 12 items and yields an overall score and 3 subscale scores, has adequate internal consistency, good overall validity, and is predictive of reduction in depressive symptoms.

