Secondary Measures: To better understand factors that may contribute to participant treatment response, the protocol has been expanded to include brief assessments for the following: insomnia, pain, illness intrusiveness, CBT skill acquisition, personality, social support, attachment style, life purpose, and Veterans perceptions. Careful consideration has been taken into selection of the measures, as not to add any undue burden on participants.

Effectiveness Data-Collection Schedule: Data will be collected over 12 months posttreatment to examine long-term effects/decay of the intervention (see Table 3). An initial telephone assessment will screen for exclusion criteria, with final eligibility determined at the baseline appointment. Four-, eight-, and twelve-month follow-up assessments will be conducted by blinded independent evaluators. A 90 minute time limit has been established for all assessment interviews in order to reduce burden on Veteran participants. For participants that do not complete all study measures during the 90 minute assessment period, participants will be

reminded that they have completed their participation. They will be provided with the option to end the call or continue the interview – not to exceed 120 minutes in total time.

Table 3. Assessment Schedule – Effectiveness Data

Aim 1 Effectiveness						
	Screen	Baseline	1 mo (bCBT only)	4 mo (post-tx)	8 mo F/ U	12 mo F/U
Chart Review, Initial PHQ-8, MINI, Cognitive Screen	P-IE or RA					
Demographics		P-IE or RA				
Charlson Index (medical comorbidities)		D				
MINI – depression, anxiety, and PTSD modules		P-IE or RA				P-IE
PHQ-9		P-IE or RA		P-IE	P-IE	P-IE
BDI-II		P-IE or RA		P-IE	P-IE	P-IE
SF-12		P-IE or RA		P-IE	P-IE	P-IE
PCL-5		P-IE or RA		P-IE	P-IE	P-IE
GAD-7		P-IE or RA		P-IE	P-IE	P-IE
Insomnia Severity Index (ISI)		P-IE or RA		P-IE	P-IE	P-IE
Illness Intrusiveness Ratings (Medical Issues)		P-IE or RA		P-IE	P-IE	P-IE
Working Alliance Inventory (Patient)				P-RA*		
Working Alliance Inventory (Clinician)				C-RA		
Cognitive-Behavioral Therapy Skills Questionnaire (CBTSQ)		P-IE or RA	P-RA*	P-RA*		
Ten Item Personality Inventory (TIPI)		P-IE or RA				
Social Support		P-IE or RA		P-IE or RA	P-IE or RA	P-IE or RA
Purpose of Life (PIL)		P-IE or RA		P-IE or RA	P-IE or RA	P-IE or RA
Attachment		P-IE or RA				
VA Perceptions		P-IE or RA		P-IE or RA		
Expectancy Rating Scale (ERS)			P-RA*			
Pain – 2 questions		P-IE or RA		P-IE	P-IE	P-IE

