Other analyses: Prediction of bCBT Treatment Response: We will use multivariate analyses to predict treatment response in the bCBT group, defined as 50% or greater reduction in PHQ-9 and BDI scores from baseline to posttreatment. Variables will include patient demographic and clinical characteristics (e.g., baseline depression severity, mental health comorbidities, treatment expectancy), as well as treatment (number of sessions attended, therapeutic alliance, patient engagement) and clinician factors (e.g., clinician adherence/skillfulness). Depression Treatment Intensity: Within the bCBT treatment group, the study team will evaluate the associations between depression-symptom response and treatment intensity (number of sessions). We will explore potential patient demographic and clinical characteristics associated with treatment response and intensity. Further, we will use surveys and qualitative interviews

with clinicians and bCBT participants to more fully understand whether the treatment intensity received was the treatment believed to be ideal. Perspectives from both patients and providers will be needed to fully understand this construct.

All exploratory analyses will occur exclusively at the Houston HSR&D CoE under the direction of the PI ([name]), study statistician (Co-I [name]), and study data analyst ([name]).

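### Exploratory Aim A predicts bCBT response partly from variables measured during or after treatment, which may themselves reflect that response

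*Combined protocol and SAP*

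**What the plan says.** Section 3.0 lists prediction of bCBT response from patient, treatment and clinician variables as Exploratory Aim A. Section 5.6, under Other analyses, says the team will "predict treatment response in the bCBT group, defined as 50% or greater reduction in PHQ-9 and BDI scores from baseline to posttreatment". It groups the candidate variables in two relevant ways. The first group is patient characteristics: "Variables will include patient demographic and clinical characteristics (e.g., baseline depression severity, mental health comorbidities, treatment expectancy". The second follows directly: "as well as treatment (number of sessions attended, therapeutic alliance, patient engagement". Clinician factors complete the list.

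Section 5.5 fixes when these are measured:

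- **Expectancy.** The Table 3 row "Expectancy Rating Scale (ERS") has one entry, in the 1-month bCBT-only column. Screen and Baseline are empty.
- **Alliance.** The row "Working Alliance Inventory (Patient") and the matching clinician row each have one entry, at 4 months (post-treatment).
- **Engagement.** "Therapist Rating of Patient Engagement and Adherence will be collected following the last session of treatment".

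Section 5.1 describes the treatment course. "Clinicians will be encouraged to offer 6 weekly treatment sessions", with room to vary. Those who respond rapidly are treated for a short course: "responders will be asked to stay in treatment for a minimum of 3 sessions". Clinicians are asked to take the PHQ-9 in sessions and to discuss response with the patient. Reaching the 50% benchmark leads the clinician to raise stopping, and non-response allows extension to as many as 9 sessions.

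**The concern.** A variable can be said to predict response only if it was fixed before the response it predicts. Four of the listed variables may fail that test. By 1 month a patient may have had several sessions and seen PHQ-9 results, so the expectancy score can mix prior belief with experienced benefit. At 4 months patient and clinician rate the alliance when both may know whether treatment worked, and the therapist rates engagement with the same knowledge. Session count follows from response through the rules for ending or extending treatment.

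An association found in such a model could run from response to the variable, from the variable to response, or both. If the results are written up as predictors of response, a reader could conclude that raising expectancy or strengthening alliance improves outcome when the data are equally compatible with the reverse. Session count could mislead the other way: early responders may stop sooner, which could hide a benefit of more treatment.

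**Working it through.** The plan gives no power or error figure for this analysis, so there is none to reproduce. The check has three parts.

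**1. Order of measurement against the outcome (4-month PHQ-9 and BDI-II)**

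| Variable in 5.6 | When measured | Position |
|---|---|---|
| Demographics, baseline severity, baseline comorbidities | Baseline | Before treatment |
| Expectancy (ERS) | 1 month, bCBT only | Probably during treatment; clock start not stated |
| Alliance, both forms | 4 months | Same time point as outcome |
| Engagement rating | After last session | After treatment |
| Number of sessions | Accrues over treatment | Depends on response |

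**2. Sessions possible by 1 month**

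One month is 30.4 / 7 = 4.34 weeks. With weekly sessions, a patient whose first session is 0, 1, 2, 3 or 4 weeks after the clock starts can have had 5, 4, 3, 2 or 1 sessions. With a minimum of 3 sessions, some rapid responders could have finished before expectancy is scored. If the clock runs from baseline or randomization and the first session is late enough, the score could fall at or before session 1.

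**3. How often would a measure with no causal effect look predictive?**

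Inputs:

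- n = 104 bCBT patients. From 5.6, 70 × 1.48 = 103.6, the number left after the planned 25% attrition from 138.
- Response rate p = 0.35 (assumed).
- Correlation r of the measure with improvement so far: 0.2, 0.3 or 0.4 (assumed).
- Share s of the variance in final change already accrued when the measure is taken: 0.25 or 0.50 at 1 month (assumed), 1 at post-treatment.
- Two-sided 5% test, 3,000 simulated trials per cell.

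| Timing | r = 0.2 | r = 0.3 | r = 0.4 |
|---|---|---|---|
| 1 month, s = 0.25 | 13% (OR 1.19) | 21% (1.27) | 35% (1.40) |
| 1 month, s = 0.50 | 20% (1.25) | 42% (1.43) | 63% (1.64) |
| Post-treatment, s = 1 | 36% (1.40) | 68% (1.69) | 90% (2.06) |

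Odds ratios are per SD. With r = 0 the rate is about 5%.

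A closed form agrees. The correlation with final change is r√s. Dichotomizing at 35% multiplies it by φ(z)/√(p(1−p)) = 0.370 / 0.477 = 0.777. Power is then approximately Φ(atanh(r_b)·√(n−3) − 1.96).

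- *Lowest 1-month cell:* r_b = 0.2 × 0.5 × 0.777 = 0.078. Adding the small opposite tail gives 12%.
- *Highest 1-month cell:* r_b = 0.4 × 0.707 × 0.777 = 0.220, giving 61%.
- *Post-treatment:* r_b = 0.155 and 0.311 give 35% and 90%.

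The n of 104 reflects 12-month attrition, whereas this outcome is at 4 months. If all 138 were evaluable, the same formula gives 15% to 74% at 1 month and 44% to 96% at post-treatment.

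**The case against.** The strongest reply is that the aim is labelled exploratory and that 5.6 already calls alliance, engagement and session count treatment variables. It does not present them as pre-treatment characteristics, and no section proposes using them to decide whom to refer. That is fair and limits the weight of the point. It does not remove it, because 5.6 still uses them to predict response and places expectancy beside baseline severity.

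Three stronger readings are tempting, and the documents do not support them.

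- *Expectancy is scored one month into therapy.* Table 3 does not say whether the month runs from baseline, randomization or first session. The CBOC provider schedules the first session, and 5.5 treats its timeliness as something that varies.
- *These variables are consequences of response.* The documents show that they can be, not that they are. Nor is the direction wholly beyond recovery, since session PHQ-9 scores allow partial adjustment.
- *Spurious significance of about 69%.* A reader could get this by chaining correlations of 0.4 and 0.6 (r = 0.24, n = 104), but that treats the outcome as continuous. For the planned binary outcome at a 35% response rate the same r gives about 47%. Nor is it strictly a type I error: the association would be real, and the fault lies in reading it as prediction or cause.

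There is also a case for the present expectancy timing. The scale asks how logical treatment seems, and the rationale is delivered in session 1, so a score taken before session 1 is not clearly better. Finally, the protocol is dated January 2018 and enrolment was expected from March 2015 in a 4-year trial. A schedule change may therefore reach few patients. Both arguments favour an analysis fix over a new assessment schedule.

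**Conclusion.** The concern holds in this form: the planned model mixes pre-treatment variables with four that may partly reflect response, and the plan does not separate, order or adjust them. The alliance, engagement and session-count parts do not depend on when the 1-month clock starts; the expectancy part does. The sizes (about 13% to 63% at 1 month, 36% to 90% at post-treatment) illustrate what could happen. They rest on assumed correlations, an assumed share of early change and an assumed 35% response rate, none of which the documents give. Demographics, baseline severity and baseline comorbidities are untouched, as is the randomized comparison in Aim 2. What changes is what Exploratory Aim A can conclude.

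**What to change.** In the prediction paragraph of 5.6:

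1. Fit the prediction model on variables measured before treatment: demographics, baseline severity and baseline comorbidities.
2. Analyse the Working Alliance forms, therapist-rated engagement and number of sessions separately, and report them as concurrent or process correlates of response, not predictors.
3. Take expectancy out of the baseline characteristics. Adjust the 1-month score for the session PHQ-9 change recorded up to that contact, and label it as not pre-treatment. State in Table 3 when the 1-month clock starts.
4. Say which of the two analyses the clinician adherence ratings belong to, since they come from recorded sessions.

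Optionally, for remaining enrolees, add the patient Working Alliance form to the existing 1-month bCBT contact. That contact collects from participants only, so it offers no collection point for the clinician form. The earlier score would reflect only the first sessions, and a late starter might have no alliance to rate yet.

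Steps 1 to 4 use data already planned and cost a few sentences. The downside is a prediction model with fewer variables, and an expectancy adjustment that will be incomplete where session PHQ-9 scores are missing.

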Variable Length of Treatment (see Figure 1): Clinicians will provide bCBT with a flexible treatment intensity and duration, based on an innovative model described by Galovski et al.²³ In the current study each Veteran's depressive symptoms will be assessed, using an a priori PHQ-9 outcome benchmark of 50% reduction in baseline symptoms³³⁻³⁵ to determine treatment response and to provide guidance to clinicians and patients about the potential for treatment discontinuation. Clinicians are encouraged to talk about discontinuation prior to treatment completion to 1) ensure that patients continue to see value in the treatment and wish to continue the treatment 2) explore additional or alternative treatment options that may be more in line with patient needs and/or expectations. Ideally, patients will continue with the bCBT intervention but some may elect to explore other treatment options.

PHQ-9 data will inform treatment progress but will not dictate treatment discontinuation. Rather, clinicians and patients will decide on the final length of treatment (up to the maximum 9 sessions in 4 months). A response of 50% reduction in depressive symptoms was chosen, based on prior work and evidence from other studies.³³⁻³⁵ This response criterion also appropriately classifies responders with variable depression levels. A decrease in symptoms by 50% for an initial PHQ-9 of 10 (the lowest possible entry score) would require a 5-point change (the minimally clinically important difference for the PHQ-9).³⁶

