implementation strategy has been refined. The project will continue to use the ORCA with all incoming CBOC clinicians during this phase to enhance our understanding of organizational culture and needs. Quantitative data will include clinician and clinic adoption rates, clinician fidelity ratings, and bCBT utilization statistics. Qualitative methods will focus on bCBT implementation with particular emphasis on barriers, facilitators, and reaction to the implementation strategy provided by the study team. Individual interviews will be conducted with CBOC clinicians (n = 12-15), CBOC administrative staff (n = 4-5), and CBOC leadership (n = 4-5). We will also conduct individual interviews with Veterans (n = 9-12) who were randomized to the bCBT intervention. Veterans will be purposefully sampled according to bCBT exposure (no engagement, 1-3 sessions, and 4 or more sessions/completers). The study team will begin all interviews from a phenomenological perspective asking participants a broad, open-ended question about their lived experiences with bCBT, probing the salient factors and processes identified. Interviews will transition into a semi-structured format to allow for the use of probes, as suggested by Patton^{42,43} and informed by PARHIS and RE-AIM. Unlike the first two phases of formative evaluation, data collected from the PFE will be subjected to rigorous qualitative data coding and analyses. The study qualitative methodologists will then work with the larger study team to create a summary document for use during the interpretive evaluation. Interpretive Evaluation will occur during months 39-42 of the project and will seek to: 1) use a project data summary document to inform stakeholders (NAC and LAC) about preliminary study outcomes and 2) obtain stakeholder reflections on importance, meaning, and the potential for wider use of bCBT in CBOCs. To accomplish these goals, focus groups will be conducted with the NAC and LAC. Stakeholders will receive the project data summary document two weeks prior to their focus group. Focus groups will seek stakeholders' reactions to the project data using open ended questions. Follow up questions will engage stakeholders in future-oriented inquiries about implementation and dissemination potential of bCBT in CBOC settings and will attempt to obtain consensus on next steps. Focus groups will be conducted by [name] and audio recorded. Analyses will use transcript summaries rather than full coding. Focus group data will be reviewed by the full team and used to inform dissemination of project materials, manuscripts, and grant planning.

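### Session count in the bCBT arm is partly a result of response, so the planned exploratory analyses that use it to explain response are biased, in a direction that depends on who leaves early

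*Combined protocol and SAP*

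**What the plan says.** Section 5.1 (Variable Length of Treatment) sets an "a priori PHQ-9 outcome benchmark of 50% reduction in baseline symptoms" to guide the length of bCBT. On one side, "For patients who reach the response criterion, clinicians will introduce the potential for treatment discontinuation", with a requested minimum of three sessions for rapid responders. On the other, "For nonresponders, treatment may be extended up to a maximum of 9 sessions". The same section says that the PHQ-9 informs length without dictating it, that patient and clinician decide, and that a clinician may turn to other care for a patient whose needs make bCBT unsuitable.

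Section 5.5 fixes the dose variable: "Intensity/dose of bCBT will be defined as the total number of sessions attended".

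Section 5.6 (Other analyses) uses that variable twice within the bCBT arm. The prediction model for response, "defined as 50% or greater reduction in PHQ-9 and BDI scores from baseline to posttreatment", lists among its predictors "treatment (number of sessions attended, therapeutic alliance, patient engagement". The intensity analysis evaluates "associations between depression-symptom response and treatment intensity (number of sessions". Neither is given a method that allows for length having been adapted to response, or a caution about interpretation. Session-level PHQ-9 scores are to be collected (sections 5.1 and 6.0).

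**The concern.** The same 50% PHQ-9 threshold sits on both sides of the model. It helps to decide how many sessions a patient has, and it forms half of the response definition. Patients who improve early tend to have fewer sessions and those who do not improve tend to have more, whatever the sessions themselves do.

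A second force acts on the same coefficient. The plan expects some patients to attend no sessions or only a few, and treatment dropouts may remain in follow-up. If those who leave early or move to other care have a poorer prognosis, few sessions become linked to poor outcome.

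At stake is the reading of the exploratory results on prediction and treatment intensity. A coefficient for sessions will invite a conclusion about how many sessions help, and it cannot support one.

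**Working it through.** **The plan's own figure.** The dose analysis has no stated sample size, so the relevant figure is the size of the bCBT arm (section 5.6).

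- Design effect: 1 + (5.8 − 1) × 0.10 = 1.48.
- 70 × 1.48 = 103.6, taken as 104.
- Attrition of 25%: 104 / 0.75 = 138.7 (stated 138). For EUC, 70 / 0.75 = 93.3 (stated 94).
- Analysed in bCBT: 138 × 0.75 = 103.5, about 104. The 25% applies at 12 months, so more may have the 4-month outcome.

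**The check.** Data were simulated with no effect of sessions on outcome, and this model was fitted:

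logit P(response) = a + b × sessions + c × baseline PHQ-9

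The true b is 0, so the odds ratio (OR) per session, exp(b), should be 1.

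*From the documents:* stopping possible from session 3 once PHQ-9 has halved; possible extension from session 6 up to 9 otherwise; response as a 50% fall on both PHQ-9 and BDI at month 4.

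*Assumed:* mean improvement 38% (SD 30 points), baseline PHQ-9 mean 15.5, measurement SD 2, giving 27% response overall. The benchmark is followed weakly (responder stops with probability 0.25, nonresponder extends with probability 0.25), moderately (0.5, 0.5) or strongly (0.9, 0.7). A share of 0, 20 or 40% attends 0–2 sessions. The log-odds of leaving early per SD of worse prognosis is 0, 0.5 or 1.0.

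**Results, OR per extra session (true value 1)**

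| Share with 0–2 sessions | Link of poor prognosis to early leaving | Benchmark not used | Weak | Moderate | Strong |
|---|---|---|---|---|---|
| 0% | – | – | 0.35 | 0.38 | 0.39 |
| 40% | 0 | 1.00 | 0.97 | 0.93 | 0.90 |
| 40% | 0.5 | 1.16 | 1.10 | 1.04 | 0.99 |
| 40% | 1.0 | 1.33 | 1.23 | 1.15 | 1.07 |
| 20% | 1.0 | 1.36 | 1.18 | 1.06 | 0.98 |

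- With neither force present the OR is 1.00, as it should be.
- With nobody below three sessions, response was about 77% at 3–5 sessions, 28% at 6 and 13% at 7–9. With 104 analysed, 71–100% of simulated trials gave a significant result that more sessions are worse.
- With 20–40% leaving early at random, the OR was 0.84–0.97, significantly below 1 in 4–55% of trials.
- With 40% leaving early, the strong prognosis link and weak use of the benchmark (OR 1.23), 68% of trials gave a significant result that more sessions are better.
- Restricted to patients with at least three sessions, the OR was 0.35–0.41 in every setting where the benchmark was used.

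A separate simulation with its own assumed inputs gave 0.26–0.32 among patients with at least three sessions, and 0.79–1.17 overall once 20–40% attended 0–2.

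**Does a repair work?** Under the same null with no early leaving, patients still in treatment at session 6 and short of a 50% reduction were split into those who continued and those who stopped. Adjusted for baseline PHQ-9 and the session 3–6 scores, the OR for continuing was 0.99–1.01. Among patients already at the benchmark at session 3, the adjusted OR was 0.92–1.05. Adjusting for session-3 PHQ-9 but still regressing on total sessions left the OR at about 0.4.

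**The case against.** The strongest defence is that the plan claims little. The work is labelled exploratory, the intensity analysis speaks only of associations, and no aim asks how many sessions help; the second exploratory aim also rests on surveys and interviews. Response needs the BDI as well, which only study staff administer, and this loosens the link with the in-treatment benchmark. All of this stands and limits the weight of the point. It does not remove the bias, because a prediction model with sessions as a predictor still reports a coefficient that partly reflects the outcome.

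Three stronger readings are tempting, and the documents do not support them.

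- A reader might infer that response determines session count. Section 5.1 says that the PHQ-9 does not dictate length. Partial influence is enough for bias.
- A reader might infer that the analysis will show more bCBT to be worse. That holds among patients with at least three sessions, or if early leaving is unrelated to prognosis. The planned analysis covers the whole arm, and section 5.1 gives a route by which poorly suited patients leave early, so either sign is possible.
- A reader might add that section 5.5 groups "4 or more sessions/completers" whereas section 5.1 lets a completer have three sessions. The former is a sampling category for qualitative interviews. The regression uses the session count, so the label does not enter it.

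**Conclusion.** The concern holds in limited form. Session count is partly a consequence of in-treatment response, section 5.6 uses it to explain response, and nothing in the plan deals with the feedback. With no true dose effect, the OR per session is about 0.3–0.4 among patients with at least three sessions and roughly 0.8–1.2 in the whole arm. The planned coefficient can therefore be significant in either direction when sessions do nothing.

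These sizes rest on assumed improvement, early leaving and use of the benchmark, none of which the documents give. That the coefficient cannot be read as a dose effect follows from the text alone. Only the exploratory analyses are affected. The Aim 2 comparison is by intention to treat, and the number of bCBT sessions is not among its listed covariates. The change is worth making, but the trial's main conclusion does not depend on it.

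**What to change.** Amend section 5.6 (Other analyses) in three places.

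1. Remove total sessions attended from the response-prediction model and use predictors fixed at baseline. Expectancy and CBT skills at 1 month come after about four weekly sessions and may already reflect early response; say so if they are kept. Alliance (month 4) and therapist-rated engagement (after the last session) have the same timing problem.
2. For intensity, use the session PHQ-9 scores in a landmark analysis. At a pre-stated session, such as 3 or 6, take patients still in treatment and compare those who continue with those who stop, adjusting for baseline PHQ-9 and all PHQ-9 scores up to that session. Do not stratify by, or regress on, the final number of sessions. In a null simulation, mean PHQ-9 change per session was about −2.2 for patients ending at 3–5 sessions, −0.7 to −1.1 at 6, and −0.5 to −0.7 at 7–9, which is a false pattern favouring fewer sessions.
3. Report the raw session-response association as descriptive, with a statement that it is not a dose effect.

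The cost is SAP wording and slightly more analysis on data already planned. Patients who leave before the landmark are excluded, so the result says nothing about them. Validity also requires that the decision to continue depends on the recorded PHQ-9; where it turns on unrecorded reasons, some bias will remain.
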